Registry and trial number	EU Clinical Trials: 2022-501304-10-00, ClinicalTrials.gov: NCT05564130		
Date of registration	EU Clinical Trials: Sept. 26, 2022, ClinicalTrials.gov: Oct. 3, 2022		
Funding	Novo Nordisk Foundation		
Primary sponsor	[name], Aarhus University		
Contact	[name], [contact]	k	
Title	Bicarbonate for In-Hospital Cardiac Arrest (BIHCA) – A Randomized, Double- Blind, Placebo-Controlled Trial		
Country of recruitment	Denmark		
Condition studied	In-hospital cardiac arrest		
Interventions	Sodium bicarbonate 50 ml (1 mmol/ml) for up to two doses		
Comparator	Placebo 50 ml (0.9% NaCl) for up to two doses		
Inclusion criteria	 In-hospital cardiac arrest Age ≥ 18 years Received at least one dose of adrenaline during cardiac arrest 		
Exclusion criteria	 1) Clearly documented "do-not-resuscitate" order prior to the cardiac arrest 2) Prior enrollment in the trial 3) Invasive mechanical circulatory support at the time of the cardiac arrest 4) Known or suspected pregnancy at the time of the cardiac arrest 5) Known objection by the patient to participate in the trial 6) Clinical indication for bicarbonate administration 		
Study type	Interventional	Allocation: Randomized (1:1)	
	Intervention model: Parallel group	Masking: Double-blind	
Date of first screening	February 6 th , 2023		
Target sample size	778		
Recruitment status	Recruiting		
Primary outcomes	Return of spontaneous circulation		
Key secondary outcomes	Survival at 30 days		
	Survival at 30 days with a favorable neuro Scale 0-3)	ological outcome (modified Rankin	

Steering committee

[name]., M.P.H., Ph.D., D.M.Sc. Department of Anesthesiology and Intensive Care Aarhus University Hospital

[name]., M.P.H, Ph.D. Research Center for Emergency Medicine Aarhus University Hospital

[name]. Research Center for Emergency Medicine Aarhus University Hospital

[name]., Ph.D. Department of Anesthesiology Copenhagen University Hospital – Rigshospitalet

[name]. Department of Anesthesiology Odense University Hospital

[name]., Ph.D. Department of Cardiology Aalborg University Hospital

[name]., D.M.Sc. Department of Cardiology Copenhagen University Hospital – Herlev

[name]., Ph.D. Department of Cardiology Copenhagen University Hospital – Gentofte [name]., Ph.D., D.M.Sc. Department of Anesthesiology and Intensive Care Aarhus University Hospital

[name]. Prehospital Emergency Medical Services Central Denmark Region

- Change of investigators at Slagelse Hospital
- Change of site investigator at Hvidovre Hospital
- Correction noting that data will be saved for 25 years (section 7.3)

Version 1.2 (Sept. 27th, 2022) to version 1.3. (Oct. 19th, 2022)

- Addition of ClinicalTrials.gov number and changed the registration date
- Addition of anticipated date of first screening
- Clarified the definition of in-hospital (section 4.2)
- Changed "bicarbonate" to "standard bicarbonate" (section 5.3)
- Modifications to section 9.3.3 and minor modifications to 9.3.4
- Addition of pictures of the trial kit and minor updates to the design of the labels (Appendix 1)

Version 1.1 (Sept. 5th, 2022) to version 1.2 (Sept. 27th, 2022)

- Addition of trial registration dates to the trial overview/synopsis
- Addition of secondary Bayesian analyses (section 6.2.10)
- Modifications to section 9.3.3

BIHCA Protocol – version 1.5 Page **19** of **84** • Appendix 4 removed

Version 1.0 (July 8th, 2022) to 1.1 (Sept. 5th, 2022)

- Correction of minor typos and investigator names
- Change of investigator [name] to [name]
- Added justification for providing the trial drug as a bolus (section 3.3)
- Clarification of the power in the sample size calculation (section 6.1)
- Added that patients who withdraw consent will not be replaced (section 6.1)
- Clarification that the clinician will determine exclusion criteria #6 in real-time (section 4.3)
- Added a definition of the end of the trial (section 9.3.6)
- Section 9.4 regarding "low-intervention trial" has been removed
- Clarification that the sponsor will allow monitoring from relevant authorities (section 10.1)
- Statement regarding publication of the results on the CTIS portal (section 12)
- Clarification that the funding has been paid to an account at Aarhus University (section 14)

1. BACKGROUND

1.1 In-hospital cardiac arrest

1.1.1 Incidence and mortality

In-hospital cardiac arrest (IHCA) is relatively common with approximately 2,000 cases in Denmark⁷ and 300,000 cases in the United States⁸ each year. Unfortunately, outcomes remain poor with 50-70% achieving return of spontaneous circulation (ROSC) and only 25-30% surviving to hospital discharge.^{7,9,10} Furthermore, in initial survivors, there are substantial post-discharge morbidity and early mortality.¹¹⁻¹³

1.1.2 An understudied entity

Clinical trials are sparse in cardiac arrest^{14,15}, and especially in IHCA^{9,16}, relative to the burden of the condition. In a systematic review of all randomized clinical trials involving cardiac arrest from 1995 to 2014, Sinha et al. found that 81 (88%) were exclusively in out-of-hospital cardiac arrest (OHCA), 7 (8%) involved OHCA and IHCA, and only 4 (4%) involved exclusively IHCA. The total number of included patients were 83 times higher in OHCA studies as compared to IHCA studies.¹⁷ A systematic search conducted in 2018 identified only 23 trials that included patients with IHCA published within the last 30 years.⁹ Of these, only two trials included more than 500 patients.⁹

There is a scarcity of evidence-based pharmacological interventions for IHCA.^{18,19} The evidence for adrenaline (epinephrine) and amiodarone, the only two drugs currently recommended, is limited and based on extrapolation from OHCA.²⁰⁻²² There is therefore a need for additional randomized clinical trials in IHCA in order to advance the science and improve patient outcomes.

1.1.3 Pathophysiology

In broad terms, cardiac arrest can be divided into three phases: pre-cardiac arrest, intra-cardiac arrest, and post-cardiac arrest, in which intra-cardiac arrest can be further divided into a no-flow (no circulation) and a low-flow (circulation induced by chest compressions) phase. One of the main drivers of poor outcomes after cardiac arrest is the duration of the cardiac arrest (i.e., no-flow and low-flow time); for each minute increase in the length of the cardiac arrest, mortality substantially increases.²³⁻²⁵ Because of this, and since ROSC is a prerequisite for more long-term survival, the goal of most intra-cardiac arrest interventions is to establish ROSC and limit the duration of the cardiac arrest.

The pathophysiology of cardiac arrest and the post-cardiac arrest syndrome is complex and has been described in extensive details elsewhere.²⁶⁻²⁸ Ischemia during the cardiac arrest and subsequent ischemia-reperfusion injury activates multiple harmful pathways including systemic inflammation, endothelial

activation, activation of immunological and coagulation pathways, adrenal insufficiency, mitochondrial damage, and microvascular dysfunction.²⁶ Consequently this leads to a clinical state (the post-cardiac arrest syndrome) with global brain injury, impaired myocardial function, macrocirculatory failure, and increased susceptibility to infections.²⁶ Patients are often hemodynamically unstable following a cardiac arrest and early post-cardiac arrest hypotension is strongly associated with poor outcomes.²⁹

1.1.4 Acidosis during cardiac arrest

In a healthy individual, the pH of the blood is tightly regulated to maintain homeostasis. The acid-base status is maintained by intra- and extracellular buffer systems, pulmonary excretion of volatile acids (i.e., CO₂), and by renal excretion of fixed acids. During cardiac arrest, the inability to exhale CO₂ and the production of acids due to decreased perfusion and tissue hypoxia results in a substantial decrease in pH (acidosis). With initiation of chest compressions and ventilation, the excess CO₂ is partly excreted, and the acidosis is therefore often primarily metabolic.³⁰

Studies have demonstrated the presence of severe acidosis during and after IHCA^{31,32}, with many patients also being acidotic prior to the cardiac arrest³³. In our recent VAM-IHCA trial³⁴, we found a mean pH after ROSC of 7.05 (standard deviation: 0.18) indicating severe acidosis. 98% of the patients had a pH below 7.35 (defined as acidosis), 35% of the patients had a pH below 7.0 and 21% had a pH below 6.9. A higher pH was strongly associated with better outcomes. For every 0.1 increase in pH, the odds of 30-day survival were increased by 1.33 (95%CI: 1.07, 1.62), while adjusting for potential confounders (age, witnessed status, initial rhythm, duration of the cardiac arrest). The strong relationship between pH and 30-day survival is illustrated in Figure 1. Our findings are consistent with a previous study showing that more severe acidosis is associated with worse outcomes.³¹

[figure not shown]

Figure 1. Association between pH and survival

Severe acidosis has a number of important detrimental effects during cardiac arrest: 1) Acidosis decreases cardiac contractility by interfering with almost every step in the excitation–contraction coupling, 2) the effect of catecholamines (e.g., adrenaline) is attenuated by acidosis, and 3) severe cerebral acidosis enhances ischemic brain damage.^{30,35} Based on the detrimental effects of acidosis, administration of bicarbonate as a buffering strategy during cardiac arrest is promising.

1.2 Bicarbonate

1.2.1 Mechanism

According to the Henderson–Hasselbalch approach to acid-base status, bicarbonate (HCO_3^-) administration results in an increase in pH (i.e., decrease in H⁺) and production of CO_2 :

$$H^+ + HCO_3^- \leftrightarrow H_2CO_3 \leftrightarrow CO_2 + H_2O$$

Considering Stewart's approach to acid-base status, sodium bicarbonate administration increases pH by increasing the strong ion difference. Although these different mechanisms are debated, administration of sodium bicarbonate indisputably causes an increase in pH. Given this effect, we postulate, that during cardiac arrest with severe acidosis, the administration of bicarbonate will increase pH and counteract the negative consequences of acidosis (section 1.1.4), improve the chance of ROSC, and ultimately improve more long-term outcomes.

1.2.2 Animal studies

Multiple animal studies have investigated the role of bicarbonate during cardiac arrest. In large animal models (pigs and dogs) published within the last 30 years, results have been inconsistent with some studies

BIHCA Protocol – version 1.5 Page **23** of **84** showing harm^{36,37}, some finding no effect³⁸⁻⁴⁰, and some finding a beneficial effect⁴¹⁻⁴⁴. The results are difficult to interpret for multiple reasons: 1) The animals had no underlying disease, often had short cardiac arrests, and the degree of acidosis was often less severe when compared to the human condition, 2) all of the studies were conducted more than 20 years ago with limited standardization of the methodology and concurrent therapies, and 3) some studies used very large doses of bicarbonate resulting in (severe) alkalosis, which is inconsistent with bicarbonate use in humans.

[figure not shown]
1.2.3 Human studies

[figure not shown]
Recent systematic reviews have described the literature related to bicarbonate and outcomes in patients with cardiac arrest.⁴⁵⁻⁴⁷ A meta-analysis of observational studies found no effect of bicarbonate administration on outcomes.⁴⁵ However, these observational studies are at a very high risk of bias due to confounding and "resuscitation time bias". Resuscitation time bias is a unique methodological concept in the setting of cardiac arrest.^{48,49} This is a severe bias that occurs when an intervention is compared to no intervention during cardiac arrest without consideration of the timing of the intervention. Briefly, this occurs because patients with longer cardiac arrests are more likely to receive a given intervention and they are also more likely to die irrespective of the intervention. This will bias any comparison against the intervention.^{48,49} The results from these observational studies are therefore very difficult to interpret.

Three randomized trials have compared bicarbonate administration to placebo during cardiac arrest.⁵⁰⁻⁵² An overview of the trials is provided in Table 1 and meta-analytic results for survival to intensive care unit (ICU) admission are provided in Figure 2.

Table 1. Overview of randomized clinical trials of bicarbonate					
Trial	Inclusion	Years	Sample size	Intervention	Time to drug
	OHCA, ventricular				
Dybvik, 1995 ⁵⁰	fibrillation or asystole,	1987-1994	502	250 ml Tribonat*	Not reported
	cardiac origin				
Vukmir, 2005 ⁵¹	OHCA, shockable, non-	1994-1998	1994-1998 874	Mean ≈ 70 mmol	Not reported
	respiratory		074	bicarbonate	Not reported
	OHCA, admitted to ED,				
Ahn, 2018 ⁵²	pH < 7.1 or bicarbonate	2015	50	50 mmol	31 minutes
	< 10 mEq/L				

* Sodium bicarbonate 160 mmol/l, trometamol 300 mmol/l, disodium phosphate 20 mmol/l, and acetate 200 mmol/l

As can be seen in Figure 2, these trials found no benefit or harm of bicarbonate administration for patients with OHCA. These results are very difficult to generalize to contemporary IHCA. First, the two largest trials were conducted more than 20 years ago, where cardiac arrest management and outcomes were very different. Second, the trials all included patients with OHCA. As we have described in previous manuscripts, there are important differences between IHCA and OHCA.^{9,53} Most notable is the fact that advanced interventions, including drugs, are administered much earlier in the in-hospital setting. For example, in our recent trials, the drug intervention was administered after a median of 8 minutes in the inhospital setting but after a median of 18 minutes in the out-of-hospital setting.^{34,54} Although time to trial drug was not reported in the two larger trials, it was 31 minutes in the trial by Ahn et al.⁵² It is highly unlikely that any drug will have an effect when administered this late. Moreover, given that patients with IHCA are often deteriorating prior to the cardiac arrest³³, patients with IHCA are more likely to be severely acidotic. The Dybvik et al. trial reported a mean pH of 7.23 after the cardiac arrest in the placebo group⁵⁰, whereas we found a mean pH of 7.05 in our recent trial as described in section 1.1.4.

1.2.4 Recommendations and clinical use of bicarbonate

Current European and American guidelines do not recommend the routine use of bicarbonate for patients with cardiac arrest except in specific circumstances such as hyperkalemia and certain toxicological causes of cardiac arrest.^{18,55,56}

Despite these recommendations, bicarbonate is commonly used during cardiac arrest. The best available data comes from a large, multicenter registry of IHCA in the United States. In a publication from 2018 using this registry, we found that bicarbonate was used in approximately 50% of all IHCAs with an increase in use from 2001 to 2016 (Figure 3).⁵⁷ This corresponds to approximately 150,000 patients in the United States receiving bicarbonate during IHCA each year.^{8,57} We have found similar results for pediatric cardiac arrest, where more than 50% of children with an IHCA in the United States receive bicarbonate.⁵⁸

[figure not shown]

Figure 3. Use of bicarbonate for IHCA in the United States

Data on the use of bicarbonate from outside the Unites States are sparse. In our recently published VAM-IHCA trial, bicarbonate was administered to 9% of all included patients.³⁴ A recent study from Taiwan found that bicarbonate was administered in 69% of patients with IHCA.⁵⁹

1.2.5 Use of bicarbonate outside of cardiac arrest

Sodium bicarbonate is approved and used for treatment of metabolic acidosis⁶⁰ and is commonly administered to acute and critically ill patients for this indication^{61,62}. There is limited data from clinical trials to support the use of bicarbonate in the intensive care unit. However, results from a randomized clinical trial suggested that bicarbonate could be beneficial in patients with acute kidney injury and metabolic acidosis (pH < 7.20).⁶³ Bicarbonate treatment for this indication is included in the Surviving Sepsis Campaign.⁶⁴ In contrast, the Surviving Sepsis Campaign suggest against the use of bicarbonate for acidosis related to elevated lactate based on very limited evidence from small cross-over trials showing no benefit of this therapy.⁶⁴

1.2.6 Potential theoretical concerns

Although the positive effects of bicarbonate appear promising, some theoretical concerns have been raised.⁶⁵ These primarily include a risk of hypernatremia/hyperosmolarity, decreased coronary and cerebral perfusion pressures, and intracellular acidosis. Many of these concerns are based on a few old animal studies such as a 1991 cardiac arrest study by Kette et al.³⁶ This study used a very high dose of bicarbonate (2.5 mmol/kg) and did not administer adrenaline making the results difficult to interpret.³⁶ Multiple subsequent animal and human studies have not reported severe hypernatremia or a decrease in perfusion pressures

BIHCA Protocol – version 1.5 Page **26** of **84** with administration of bicarbonate.^{38-40,66} The theoretical risk of transient intracellular acidosis is postulated to be caused by a production of excess CO₂, which is freely diffusible into cells and therefore might contribute to intracellular acidosis. However, this is based on studies utilizing very high doses of bicarbonate and providing no ventilation. This theory is not supported by other studies that demonstrate either an increase or no change in intracellular pH.^{67,68}

1.3 Standard of care

The standard of care during cardiac arrest is described by guidelines from the European Resuscitation Council.¹⁸ Pharmacological treatment is generally limited to amiodarone/lidocaine and adrenaline for patients with a refractory shockable rhythm and adrenaline for patients with a non-shockable rhythm.¹⁸ Although the evidence for amiodarone/lidocaine and adrenaline is limited and controversial²⁰⁻²², these drugs are currently recommended and are given, when applicable, to most patients with cardiac arrest. The intervention of the present trial (sodium bicarbonate) will therefore be compared to placebo and both groups will receive the established standard of care.

2. TRIAL OBJECTIVES AND HYPOTHESES

Primary objective: To determine whether sodium bicarbonate as compared to placebo, when administered during IHCA, will increase ROSC.

Hypothesis: Sodium bicarbonate administered during IHCA will increase ROSC.

Secondary objective: To determine whether sodium bicarbonate as compared to placebo, when administered during IHCA, will increase survival at 30 days and survival at 30 days with a favorable neurological outcome.

Hypothesis: Sodium bicarbonate administered during IHCA will increase survival at 30 days and survival at 30 days with a favorable neurological outcome.

3. TRIAL DESIGN

3.1 Overview

This is an investigator-initiated, multicenter, randomized, placebo-controlled, parallel group, double-blind, superiority trial of sodium bicarbonate during adult IHCA. There will be 21 enrolling sites in Denmark. 778 adult patients with IHCA receiving at least one dose of adrenaline will be enrolled. The primary outcome is ROSC and key secondary outcomes include survival at 30 days and survival at 30 days with a favorable neurological outcome.

3.2 Allocation

Patients will be randomized in a 1:1 ratio to either sodium bicarbonate or placebo in blocks with random sizes of 2, 4, or 6. The randomization will be stratified according to site.⁶⁹ An independent statistician will create the randomized allocation list using a random number generator. The list will only be shared with the pharmacy, which will not be involved in clinical care. The pharmacy and the independent statistician will both store the randomization list. As described in section 3.3 and section 3.4, sites will be provided with numbered blinded kits including either sodium bicarbonate or placebo ensuring allocation concealment.

3.3 Interventions

3.3.1 Sodium bicarbonate

The trial drug will consist of 50 ml of 1 mmol/ml sodium bicarbonate (ATC code: B05XA02) given as soon as possible after the first dose of adrenaline. If the patient remains in cardiac arrest, one additional dose of 50 ml of 1 mmol/ml sodium bicarbonate will be administered after the second dose of adrenaline dose for a maximum of two doses.

When sodium bicarbonate is administered during cardiac arrest for special circumstances (e.g., hyperkalemia or tricyclic antidepressant overdose), a dose of 1-2 mmol/kg or 50 mmol is usually recommended.^{55,56} It is not feasible to accurately dose sodium bicarbonate based on weight during a cardiac arrest as the weight is often unknown and drugs need to be administered quickly. Therefore, up to two doses of 50 mmol sodium bicarbonate for a total of 100 mmol has been chosen. In our previous VAM-IHCA trial, which had similar inclusion and exclusion criteria³⁴, the median weight of the included patients was 78 kg (1st and 3rd quartiles: 67, 92). With this weight, a dose of 100 mmol corresponds to 1.3 mmol/kg (1st and 3rd quartiles: 1.1, 1.5). A previous trial found that a dose of 50 mmol sodium bicarbonate increased pH with 0.16 compared to placebo.⁵² Based on this, and the severity of acidosis seen during cardiac arrest (see section 1.1.4), we consider a maximum dose of 100 mmol sodium bicarbonate to be appropriate. Given the

urgency of cardiac arrest, it is essential that the medication is administered quickly (i.e., as a bolus). This is consistent with clinical practice and international guidelines.^{55,56} We note that some patients might only receive one dose of the trial intervention as resuscitation is terminated or the patient achieves ROSC. In our previous IHCA trial, 28% of the included patients only received one dose of the trial medication.³⁴

3.3.2 Placebo

The placebo will consist of 50 mL of 9 mg/mL NaCl ("normal saline") from containers identical to the sodium bicarbonate containers. Normal saline is often administered to critically ill patients and has no known effects or side-effects with these small volumes.

3.3.3 Procedures

The drugs will be produced, managed, and stored according to all relevant guidelines and regulations. The trial drugs will be placed in a blinded trial kit (a small box, see Appendix 1) containing two glass vials each with 50 ml of sodium bicarbonate (1 mmol/ml) or corresponding placebo (0.9% NaCl). The trial kits will be prepared at the Capital Region Pharmacy, a company that specializes in the production of medicine and is approved by the Danish Health authorities and shipped to the participating sites regularly. The trial kit will be stored at room temperature and brought to the IHCA by a designated member of the cardiac arrest team. Once it is anticipated that the patient will receive at least one dose of adrenaline, the trial kit will be opened, and the patient will be considered randomized. A designated member of the cardiac arrest team will then prepare the trial drugs. The cardiac arrest team members will have training in the trial and drug administration procedures (see section 3.5.2). We expect that these procedures will take approximately 1 minute and that they will not interfere with the clinical management of the patient. Once prepared, 50 ml of the trial drug will be administered after the second dose of adrenaline. If a patient achieves ROSC while the drug is being administered, the remaining volume of the drug will be provided. The trial drug can be administered either intravenously or intraosseously.

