Other potential side effects have been described with the administration of sodium bicarbonate, including headache, muscle pain, nausea and vomiting, and vertigo.^{60,101} However, given that patients with cardiac arrest are unconscious, these cannot be assessed and are of limited relevance.

Accidental subcutaneous injection of sodium bicarbonate can result in tissue necrosis.¹¹² However, the trial drug is given immediately after adrenaline, which carries a similar risk and hence the same precautions; a misplaced peripheral catheter should be recognized here. The risk of necrosis due to the intervention is therefore minimal.

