The current trial fulfils all the above criteria as described in section 9.1 for (b) and section 9.2.3 for (a) and (c)-(f). Under these circumstances, research with pharmacological interventions is allowed if 1) informed consent to continue participation in the clinical trial is obtained from the patient or the legally designated representative without undue delay, and 2) the patient or the legally designated representative is informed of the right to object to the use of trial data if consent for continuation in the trial is not provided.²

9.2.3 Regulatory conditions in relation to the current trial The current trial fulfills all criteria listed in section 9.2.2:

Condition (a)

IHCA is an unpredictable and sudden event. It is therefore impossible to obtain consent prior to the event. During the cardiac arrest, patients are unconscious and therefore not able to provide consent.

Condition (c)

The intervention will be administered as soon as possible after the administration of the first dose of adrenaline. In our previous VAM-IHCA trial, the trial drug was administered after a median of 8 minutes (first and third quartiles: 6, 12).³⁴ Given these time frames, it would be impossible to obtain informed consent from a legally designated representative.

BIHCA Protocol – version 1.5 Page **50** of **84**

Condition (d)

IHCA is sudden and often unexpected, and it is unlikely that participants will have objected to participation in a clinical trial should they have a cardiac arrest. In our previous trials involving cardiac arrest patients, all patient and legally designated representatives provided consent for future participation.^{34,54} However, in the unlikely event that a participant has clearly objected to participation in the trial prior to their cardiac arrest and the clinician including the patient is aware of this objection, the patient will not be included (see section 4.3).

Condition (e)

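### Section 3.3.3 times the prepared trial drug after the second adrenaline dose and omits the first-adrenaline dose set in 3.3.1 and 9.2.3

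*Protocol*

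**What the plan says.** Section 3.3.1 sets the schedule. The first 50 ml is "given as soon as possible after the first dose of adrenaline". If the patient is still in arrest, "one additional dose of 50 ml of 1 mmol/ml sodium bicarbonate will be administered after the second dose of adrenaline dose", and two doses is the maximum.

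Section 9.2.3, condition (c), gives the same timing when it argues that prior consent is impossible: "The intervention will be administered as soon as possible after the administration of the first dose of adrenaline".

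Section 3.3.3 describes what the arrest team does. The kit is "containing two glass vials each with 50 ml of sodium bicarbonate (1 mmol/ml") or matching placebo. When at least one adrenaline dose is expected, "the trial kit will be opened, and the patient will be considered randomized". A team member then prepares the drug, which is expected to take about one minute. The dosing instruction follows: "Once prepared, 50 ml of the trial drug will be administered after the second dose of adrenaline". The rest of the section covers finishing the volume if ROSC occurs during administration, and the route. It never mentions a dose after the first adrenaline.

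Two other places describe the regimen without saying which adrenaline dose comes first. The synopsis has "Sodium bicarbonate 50 ml (1 mmol/ml) for up to two doses", and section 5.4.3 says "the trial drug is given immediately after adrenaline, which carries a similar risk".

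**The concern.** The protocol gives two different times for the start of its intervention. One of them stands in the section that describes the bedside procedure. Section 3.5.2 cites 3.3.3, together with 9.3.2, for the procedures that clinical staff are taught, and section 3.3.4 cites 3.3.3 for actual drug administration. The sentence is therefore an operative instruction and not background text.

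Two things would follow if a team acted on it:

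- **Later first dose.** Early delivery is part of the trial's rationale. Section 1.2.3 sets aside the earlier out-of-hospital trials partly because drugs reach patients much later in that setting. Time from arrest to first trial drug is also a predefined subgroup variable (6.2.6).
- **Patients randomized but not dosed.** Section 4.2 requires only one adrenaline dose, and randomization happens when the kit is opened. A patient whose arrest ends before a second adrenaline dose would be eligible and randomized but would have no trial dose under 3.3.3. The modified intention-to-treat set in 6.2.1 requires the first trial dose, so that patient would leave the analysis.

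**Working it through.** No disputed figure is involved, so the check is a comparison of texts.

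| Place | First 50 ml | Second 50 ml |
|---|---|---|
| 3.3.1 | As soon as possible after adrenaline dose 1 | After adrenaline dose 2, if still in arrest |
| 9.2.3, condition (c) | As soon as possible after adrenaline dose 1 | Not addressed |
| 3.3.3 | No dose tied to adrenaline dose 1 | One 50 ml dose, after adrenaline dose 2 |
| Synopsis | Up to two doses, no timing | Up to two doses, no timing |
| 5.4.3 | Immediately after adrenaline, dose not specified | Not addressed |

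**Step 1: does anything else in 3.3.3 supply the missing dose?** No. The sentence about an expected first adrenaline dose fixes when the kit is opened and the patient counts as randomized. It does not say when the drug is given.

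**Step 2: which rule is intended?** The rule in 3.3.1. It is stated in full there and repeated in 9.2.3. The synopsis allows two doses and the kit holds two vials, whereas 3.3.3 alone accounts for one 50 ml dose. A kit opened in expectation of the first adrenaline dose, and ready about a minute later, also fits poorly with waiting for the second.

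**Step 3: trace a patient who receives exactly one adrenaline dose.**

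- Under 3.3.1: eligible, randomized at kit opening, given 50 ml after that adrenaline dose, included in the modified intention-to-treat set.
- Under 3.3.3 read literally: eligible, randomized at kit opening, given nothing, excluded from that set.

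Some randomized but undosed patients can arise even under 3.3.1, because the kit is opened when adrenaline is only anticipated. The wording of 3.3.3 could only add to them.

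**Step 4: can the effect be sized?** No. That would need the share of arrests that end between the first and second adrenaline doses, the interval between those doses, and the share of teams following 3.3.3. The document gives none of these. Section 3.3.1 reports that 28% of patients in the earlier in-hospital trial received a single dose of trial medication. That counts doses of another trial's drug and is not the share with a single adrenaline dose, so it cannot stand in.

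**Step 5: does the sample size move?** The plan's figure reproduces. With 33% against 43%, two-sided alpha 0.05 and 80% power, the continuity-corrected two-proportion formula gives 389 per arm, and 2 × 389 = 778. Exact enumeration of the two-sided Fisher's exact test at 389 per arm gives 80.2% power. Correcting 3.3.3 changes none of these inputs.

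**The case against.** The strongest reply is that this is an omission and not a true contradiction. Section 3.3.1 also places a 50 ml dose after the second adrenaline dose, so the sentence in 3.3.3 can be read as describing that second dose with the first-dose clause missing. The correct rule stands two subsections earlier and again in 9.2.3. Section 3.5.2 says staff are informed about the interventions as well as the procedures and are shown correct use of the kit, and 9.3.2 refers to the whole of section 3.3. The inclusion-criterion mismatch is the same omission seen from another side. The synopsis and 5.4.3 do not say which adrenaline dose is meant, so only 3.3.1 and 9.2.3 conflict directly with the sentence.

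Most of this stands, and it limits the weight of the point. It does not make the sentence right. The sentence has no word marking a second or additional dose and no condition that the arrest continues. Its opening follows straight on from opening the kit and preparing the drug, so it reads naturally as the first administration. On the generous reading, the procedures section still lacks the first dose.

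The harm is also hypothetical. Nothing shows that any team is trained to wait. The real-time form in 7.1 records the times of first adrenaline and first trial drug and the number of doses. The draft baseline table reports both times, and the data-monitoring file in Appendix 5 carries time to first trial drug. A systematic delay would be seen.

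**Conclusion.** The concern holds, as a minor internal inconsistency. The dosing sentence in 3.3.3 is wrong as written, and the rule in 3.3.1 and 9.2.3 is the intended one. A drafting slip is the most likely cause.

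No magnitude or range can be given from the document. Dosing is blinded, so any delay or loss of patients would not favour either arm. The sample size and the analysis are unaffected.

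Confidence is high that the text is in error. That any patient has been dosed late or missed because of it is not shown. The consequences described depend on a team following 3.3.3 over two explicit statements to the contrary.

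**What to change.** Replace the dosing sentence in 3.3.3 with the full two-dose rule, for example:

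> When the drug is ready, give the first 50 ml as soon as possible following adrenaline dose one. If the arrest continues, give the other 50 ml following adrenaline dose two. Give no more than two doses in total.

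Check that the kit demonstration and the online training material state the same rule.

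The cost is one corrected sentence at the next protocol amendment and a short check of the training material. The modified intention-to-treat definition, the time-to-drug variable and the sample size need no change.
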